
Version 2 of the SAP was approved prior to the first patient visit (FPV) of the 3 additional cohorts: 2L-3L biliary tract cancer (BTC), 1L gastric or gastroesophageal junction adenocarcinoma (gastric-GEJ), and 1L non-small cell lung cancer (NSCLC). The overall changes and rationale for the changes incorporated in Version 2 are as follows:

- Add 3 additional cohorts: 2L-3L BTC, 1L gastric-GEJ, and 1L NSCLC;
- Clarify the timing of the final analysis (safety and preliminary efficacy);
- Clarify the timing of interim analyses (safety and preliminary efficacy);
- Power and sample size determinations for the 3 additional cohorts.

This version of the SAP (Version 3) corrects the illustration for the duration of response by irRECIST (Scenario 2), and was approved prior to the public disclosure of this document.

4. Study Objectives

4.1. Primary Objective

The primary objective of this Phase 1a and 1b study is to assess the safety and tolerability of 2 dosing regimens of ramucirumab plus pembrolizumab.

4.2. Secondary Objectives

The secondary objectives of this study are as follows:

- to characterize the pharmacokinetics (PK) of ramucirumab when co-administered with pembrolizumab (Phase 1a, Phase 1b)
- to assess the preliminary efficacy of ramucirumab plus pembrolizumab (Phase 1b)

4.3. Exploratory Objectives

The exploratory objectives of this study are as follows:

- to explore the association between biomarkers and clinical outcomes (Phase 1b)
- to characterize biomarker measures of immune functioning and angiogenesis (Phase 1b)
- to assess immunogenicity of ramucirumab when co-administered with pembrolizumab (Phase 1b).

5. A Priori Statistical Methods

5.1. Sample Size Determination

The primary objective for this dose-limiting toxicity (DLT) Phase 1a and Expansion Phase 1b study is to evaluate safety and tolerability. The sample size of Expansion Phase 1b was selected to allow adequate assessment of safety at the recommended doses for ramucirumab and pembrolizumab for each tumor type and dose schedule, separately.

5.1.1. Phase 1a

Phase 1a DLT Observation: up to 12 DLT-evaluable patients.

5.1.2. Phase 1b

Phase 1b Expansion: 155 patients; 15 patients each for Cohorts A and B (2L-3L gastric-GEJ), 25 patients each for Cohorts A1, A2, C, D, and E (2L-3L BTC, 1L gastric-GEJ, 2L-4L NSCLC, 2L-4L urothelial cancer, and 1L NSCLC, respectively).

The primary objective of Study I4T-MC-JVDF (JVDF) is the safety and tolerability of ramucirumab in combination with pembrolizumab. During Expansion Phase 1b, 25 to 30 patients per tumor type will be treated, to provide a preliminary assessment of tumor response and an assessment of safety. For each of the tumor types, the objective response rate (ORR) values in the simulations are provided as a reference for estimation of statistical power rather than a basis of any decision criteria. All efficacy endpoints will be utilized to determine next steps of development of the combination.

For gastric-GEJ and BTC (2L-3L), and NSCLC and urothelial cancer (2L-4L), the null hypothesis is based on the assumption that the ORR is no greater than 10% to 15% and the target treatment effect (alternative response rate) of the combination treatment on ORR is greater than 20% to 30%. Based on these assumptions, a sample size of n=25 to 30 (n=30 for combined Gastric Cohorts A and B) provides statistical power of approximately 60% to 90%, with a 1-sided nominal 0.20 significance level ([Table JVDF.1](#)).

For first-line NSCLC and gastric-GEJ, the null hypothesis is based on the assumption that the ORR is no greater than 30% to 35% and the target treatment effect (alternative response rate) of the combination treatment on ORR is greater than 45% to 55%. Based on these assumptions, a sample size of n=25 provides statistical power of approximately 65% to 90%, with a 1-sided 0.20 significance level ([Table JVDF.2](#)).

Table JVDF.1. Summary of Statistical Power for Overall Response Rates for NSCLC 2-4L, Bladder 2-4L, BTC 2-3L, and Gastric 2-3L

	NSCLC, Bladder, and BTC				Gastric (combined preliminary efficacy)			
	Low Case	High Case	Low Case	High Case	Low Case	High Case	Low Case	High Case
	N=25	N=25	N=25	N=25	N=30	N=30	N=30	N=30
Null response rate	0.10	0.10	0.15	0.15	0.10	0.10	0.15	0.15
Target response rate	0.20	0.25	0.25	0.30	0.20	0.25	0.25	0.30
Power	57.9%	78.6%	62.2%	80.7%	74.5%	90.2%	65.2%	84%

Abbreviations: BTC = biliary tract cancer; L=line; N = number of patients; NSCLC = non-small cell lung cancer.

Note: low case = 10% difference between alternative response rate and null response rate for overall response rate; high case = 15% difference between alternative response rate and null response rate for overall response rate.

Table JVDF.2. Summary of Statistical Power for Overall Response Rates for NSCLC 1L and Gastric 1L

	NSCLC (1L) and Gastric (1L; combined preliminary efficacy)			
	Low Case	High Case	Low Case	High Case
	N=25	N=25	N=25	N=25
Null response rate	0.30	0.30	0.35	0.35
Target response rate	0.45	0.50	0.50	0.55
Power	75.8%	88.5%	65.5%	81.7%

Abbreviations: 1L = First-Line; N = number of patients; NSCLC = non-small cell lung cancer.

Note: low case = 15% difference between alternative response rate and null response rate for overall response rate; high case = 20% difference between alternative response rate and null response rate for overall response rate.

5.2. Derived Endpoint Definition

5.2.1. Safety Endpoint

Safety measures that will be used in the study include adverse events (AEs), DLTs (in the Phase 1a part of the study), clinical laboratory test results, vital signs, and electrocardiogram (ECG) parameters. All AEs will be graded using the National Cancer Institute (NCI) Common Terminology Criteria for Adverse Events (CTCAE) Version 4.0. Adverse event terms will also be derived from verbatim text using the Medical Dictionary for Regulatory Activities (MedDRATM) dictionary.

5.2.1.1. Dose-Limiting Toxicity

A DLT is defined as considered to be related to study regimen by the investigator, and fulfills any 1 of the following criteria using NCI CTCAE Version 4.0:

1. Nonhematologic toxicity as follows:
 - a) Grade 4 nonlaboratory toxicity

- b) Grade 3 nonlaboratory toxicity (for example, nausea, vomiting, and diarrhea) lasting >3 days despite optimal supportive care
- c) Any Grade 3 or Grade 4 laboratory value if:
 - i. Medical intervention is required to treat the patient, or
 - ii. The abnormality persists for >1 week.

Note: Liver function abnormality: For patients with liver metastasis who begin treatment with Grade 2 aspartate aminotransferase (AST) or alanine aminotransferase (ALT), if AST or ALT increases by greater than or equal to 50% relative to baseline and lasts for at least 7 days.

- 2. Hematologic toxicity, as follows:
 - a) Grade 4 toxicity lasting ≥ 7 days, or
 - b) Grade 3 thrombocytopenia if associated with bleeding and requires platelet transfusion, or
 - c) Febrile neutropenia Grade 3 or Grade 4
- 3. Grade 5 toxicity (that is, death)
- 4. Any other significant toxicity deemed by the primary investigator and Lilly clinical research personnel to be dose-limiting, for example:
 - a) Any toxicity that is possibly related to study treatment that requires the withdrawal of the patient from the study during Cycle 1, or
 - b) A delay of >14 days due to persistent Grade ≥ 2 toxicities in initiating Cycle 2, with the exception of Grade 2 fatigue.

Any infusion or hypersensitivity reactions occurring during the infusion of the drug are not considered dose-related and therefore will NOT be considered to be a DLT.

After each of the 3 patients in a dose schedule completes the observation period, a safety analysis will occur; the data will be reviewed by study investigators and the Lilly clinical research physician/clinical research scientist (CRP/CRS), and the findings will be documented, indicating whether each dose schedule is or is not well tolerated. The results of this meeting will inform the decision whether or not to move to the expansion phase.

5.2.1.2. Exposure-Related Variables

- Cumulative dose
 - For ramucirumab, cumulative dose (mg/kg) is calculated as sum of all calculated dose levels, where calculated dose level (mg/kg) = (actual total dose [mg]) / (closest body weight [kg] prior to the treatment).
 - For pembrolizumab, cumulative dose (mg) is calculated as sum of all dose levels.

- **Duration of treatment (week)**
 - Duration of treatment (week) of ramucirumab is calculated as (date of first dose in last cycle – date of first dose + 21)/7.
 - For pembrolizumab, duration of treatment (week) is calculated as (first date of the last cycle when pembrolizumab is distributed – date of first dose + 21)/7 for pembrolizumab.

Note. Twenty-one days is added because the administration is every 21 days. In Schedule 1, ramucirumab is administered with 8 mg/kg on Day 1 and Day 8, while pembrolizumab is administered with 200 mg fixed on Day 1 every 3 weeks. In Schedule 2, ramucirumab with 10 mg/kg and pembrolizumab with 200 mg fixed are administered on Day 1 every 3 weeks. Last cycle stands for the last cycle with planned dose, regardless of whether the actual dose received is 0 or not.

- **Dose intensity** (mg/kg/week for ramucirumab or mg/week for pembrolizumab) is calculated as cumulative dose/component-specific duration of treatment in weeks.
- **Relative dose intensity (%)** is calculated as dose intensity/planned dose intensity * 100, where for Schedule 1, ramucirumab planned dose intensity = 5.3 mg/kg/week and it is 3.3 mg/kg/week for Schedule 2. The planned dose intensity = 66.7 mg/week for pembrolizumab (or according to the planned dose recorded in the electronic case report form [eCRF]).

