6.6.2. Pembrolizumab Dose Delays and Discontinuation

Adverse events (both nonserious and serious) associated with pembrolizumab exposure may represent an immunologic etiology. These AEs may occur shortly after the first dose or several months after the last dose of treatment. Pembrolizumab must be withheld (dose reductions are not permitted) for drug-related toxicities and severe or life-threatening AEs. See Section 6.9.1.3 for supportive care guidelines, including use of corticosteroids. [Table JVDF.5](#) presents the guidelines for treatment delays and discontinuation of pembrolizumab for specific AEs associated with pembrolizumab treatment.

Table JVDF.5. Pembrolizumab Treatment Discontinuation Guidelines for Specific Adverse Events at Least Possibly Related to Pembrolizumab

	Adverse Event	CTCAE Grade	Treatment Delay and Discontinuation
1	Diarrhea/Colitis	2-3	
Delay pembrolizumab until resolved to Grade 0-1.
 
 • If resolved to Grade 0-1 within 12 weeks of last dose, then resume pembrolizumab. • Within 12 weeks of last dose, if toxicity does not resolve to Grade 0-1 *or* with inability to reduce corticosteroid to ≤ 10 mg/day of prednisone or equivalent per within 12 weeks, discontinue pembrolizumab.
		4	Immediately and permanently discontinue pembrolizumab.
2	Increased AST, ALT, or Bilirubin^a	2	
Delay pembrolizumab until resolved to Grade 0-1.
 
 • If resolved to Grade 0-1 within 12 weeks of last dose, then resume pembrolizumab. • If NOT resolved to Grade 0-1 within 12 weeks of last dose, then discontinue pembrolizumab.
		3-4	Immediately and permanently discontinue pembrolizumab. See exceptions below.
3	Type 1 Diabetes Mellitus (if new onset) or Hyperglycemia associated with evidence of beta cell failure	T1DM or 3-4	
Delay pembrolizumab until patients are clinically and metabolically stable.
 
 • If clinically and metabolically within 12 weeks of last dose, then resume pembrolizumab. • If NOT clinically and metabolically stable within 12 weeks of last dose, then immediately and permanently discontinue pembrolizumab.

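### SAP 5.2.1.2 does not settle where treatment duration ends when a drug's final cycles are held, and its rounded ramucirumab denominators put full dosing slightly above 100%

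*SAP*

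**What the plan says.** SAP 5.2.1.2 computes duration of treatment in weeks, separately for each drug: an end date, minus the date of first dose, plus 21 days, all divided by 7. The end date is worded in three ways:

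- Ramucirumab formula: "date of first dose in last cycle".
- Pembrolizumab formula: "first date of the last cycle when pembrolizumab is distributed".
- Note below both formulas: "Last cycle stands for the last cycle with planned dose, regardless of whether the actual dose received is 0 or not".

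Dose intensity "is calculated as cumulative dose/component-specific duration of treatment in weeks". RDI divides that by a planned intensity. For Schedule 1, "ramucirumab planned dose intensity = 5.3 mg/kg/week and it is 3.3 mg/kg/week for Schedule 2". For the other drug, "The planned dose intensity = 66.7 mg/week for pembrolizumab", followed by a parenthesis allowing the eCRF planned dose instead. The SAP does not say whether that alternative reaches ramucirumab, or when it takes precedence.

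SAP 5.3.6 reports these variables by phase and cohort. On holds, Protocol Table JVDF.5 (section 6.6.2) says for several adverse events: "If resolved to Grade 0-1 within 12 weeks of last dose, then resume pembrolizumab".

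**The concern.** Duration is the denominator of dose intensity, so the choice of last cycle feeds directly into RDI. A held cycle has a planned dose but, on the ordinary sense of the word, no drug distributed. For a patient whose last cycles on a drug were all held, the pembrolizumab formula therefore stops at the last dosed cycle, while the note carries on to the last planned one. For ramucirumab the difficulty is different: if the note makes a zero-dose cycle the last one, the formula asks for a dose date within it, and no substitute is named.

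Two competent programmers could follow this section and report different durations and RDIs from the same data. The rounded planned intensities are a smaller, separate matter: they shift ramucirumab RDI upward by a different amount on each schedule.

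At stake is how the exposure tables are read. They support the description of tolerability, which is the study's primary objective.

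**Working it through.** **Planned intensities.** Inputs are the doses per 21-day (3-week) cycle given in SAP 5.2.1.2. The plan's figures are reproduced as one-decimal roundings. RDI at full, on-time dosing is exact intensity ÷ stated intensity.

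| Drug and schedule | Exact, per week | Stated | RDI at full dosing |
|---|---|---|---|
| Ramucirumab, Schedule 1 | 2 × 8 / 3 = 5.333 mg/kg | 5.3 | 100.63% |
| Ramucirumab, Schedule 2 | 10 / 3 = 3.333 mg/kg | 3.3 | 101.01% |
| Pembrolizumab | 200 / 3 = 66.667 mg | 66.7 | 99.95% |

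**Hypothetical pembrolizumab patient (assumed, not in the documents).** Full doses in Cycles 1 to 4, Cycles 5 to 7 planned but held, then stopped. Cycles start on Days 1, 22, 43, 64, 85, 106 and 127. The last held cycle is 127 − 64 = 63 days, or 9 weeks, after the last dose, so it lies inside the 12-week window. Cumulative dose is 4 × 200 = 800 mg.

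- Last dosed cycle: duration (64 − 1 + 21)/7 = 12 weeks; intensity 800/12 = 66.67 mg/week; RDI 66.67/66.7 = 99.95%.
- Note, last planned cycle: duration (127 − 1 + 21)/7 = 21 weeks; intensity 800/21 = 38.10 mg/week; RDI 38.10/66.7 = 57.11%.

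The same pattern for ramucirumab, with the zero-dose cycle dated by its Day 1, gives 100.63% or 57.50% on Schedule 1 and 101.01% or 57.72% on Schedule 2.

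**Range over other assumed patterns (pembrolizumab).** The last-dosed reading always gives 99.95%. The note reading is (cycles dosed ÷ cycles planned) × 99.95%.

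| Dosed / planned | Note reading | Gap, points |
|---|---|---|
| no trailing held cycle | 99.95% | 0 |
| 10 / 11 | 90.86% | 9.1 |
| 6 / 7 | 85.67% | 14.3 |
| 8 / 11 | 72.69% | 27.3 |
| 4 / 7 | 57.11% | 42.8 |
| 4 / 8 | 49.98% | 50.0 |
| 1 / 4 | 24.99% | 75.0 |

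**Effect on a cohort mean.** One patient with the 4-of-7 pattern moves the mean by (99.95 − 57.11)/15 = 2.9 points in a cohort of 15 (Cohort A or B), and by 42.84/25 = 1.7 points in a cohort of 25.

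**Unrounded denominators.** With 16/3, 10/3 and 200/3, full dosing reads exactly 100% for both drugs. The 4-of-7 patient still reads 100% or 57.1%. Rounding plays no part in that gap; only a single definition of last cycle removes it.

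**The eCRF alternative.** Suppose it also applied to ramucirumab and the eCRF recorded a reduced dose as the planned dose (both assumptions). A Schedule 2 patient at the first reduction in Table JVDF.3, 8 mg/kg, would then read 8/8 = 100% for those cycles, against 8/10 = 80% relative to the starting dose.

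**The case against.** The strongest reply is that the note controls. It defines the term both formulas use, comes after both and is not limited to one drug. The SAP also knows how to say the opposite: in 5.2.1.3 the treatment-emergent adverse event window expressly disregards zero doses, which suggests that two conventions were chosen on purpose. A zero dose may be an eCRF entry with its own date, so the ramucirumab date may exist in practice. This has force and is why *contradiction* would be too strong a word. It does not settle the matter: if the note controls, the pembrolizumab qualifier does no work, and nothing in the SAP confirms a date for a zero-dose entry.

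The other replies limit the size, and they stand:

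- A reader might infer that trailing held cycles are common. The documents give no frequency. Table JVDF.5 only permits long holds, and Protocol 6.6 asks for resumption within 21 days where possible and appropriate. A hold recorded as one delay, rather than as planned zero-dose cycles, could leave few or no trailing cycles.
- A reader might infer that full dosing generally reads 101%. That is ramucirumab on Schedule 2 alone, and the eCRF alternative may avoid the rounding where it applies.
- A reader might treat RDI as a primary tolerability measure. Protocol section 3 lists dose-limiting toxicities and safety observations, not dose intensity, and no test, sample size or decision rule uses RDI. SAP 5.3.6 also reports infusions received, delays, reductions and their reasons, with dosing listings, so held doses would not be hidden.

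**Conclusion.** The point holds as a specification gap in SAP 5.2.1.2. The wording does not fix one duration, and so not one RDI, for a patient whose final planned cycles of a drug were zero-dose. Such cycles can arise: Table JVDF.5 allows a pembrolizumab hold of up to 12 weeks from the last dose, and under Protocol 7.1 study treatment ends only when both drugs stop, so cycles can continue on one drug while the other is held.

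The gap runs from 0 to about 75 points over the assumed patterns. The pair of about 100% and 57% belongs to one of them and is not an expected result for the trial. It also rests on reading *distributed* as *given*.

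The rounding is an error as written, but of at most about 1 point: +0.63 and +1.01 for ramucirumab on Schedules 1 and 2, and −0.05 for pembrolizumab.

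The consequence is confined to supporting, descriptive exposure summaries. The documents do not support the stronger inference that the primary safety conclusions, or the decision to expand, depend on this.

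**What to change.** In SAP 5.2.1.2:

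1. Replace both end-date wordings with one rule for both drugs that follows the note: the last cycle with a planned dose of that drug, zero-dose cycles included, dated by that cycle's Day 1 visit.
2. Use the unrounded planned intensities 16/3 and 10/3 mg/kg/week for ramucirumab and 200/3 mg/week for pembrolizumab.
3. State whether and when the eCRF planned dose replaces these constants, and for which drug, so that dose reductions are not removed from RDI.

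The cost is SAP wording, plus a rerun of the exposure tables if they are already programmed. The rule needs dosing records that show which cycles had a planned dose of each drug; the documents do not let a reader check this. Reported RDI falls for patients with trailing held cycles if the last-dosed reading would otherwise have been programmed. Unrounding lowers ramucirumab RDI by up to about 1 point and raises pembrolizumab RDI by about 0.05.

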5.2.1.3. Adverse Event-Related Variables

Adverse event-related variables are listed below:

- **Dose-limiting toxicity (DLT):** Please refer to Section 5.2.1.1 for the definition of DLT.
- **Adverse event (AE)** is defined as any untoward medical occurrence in a patient administered a pharmaceutical product, without regard to the possibility of a causal relationship.
- **Treatment-emergent adverse event (TEAE)** is defined as an event that first occurred or worsened in severity between first dose of study treatment and 90 days after the last dose of study treatment and related SAEs reported beyond 90 days after the last dose of study treatment, where last dose stands for actual dose, that is, 0 dose is not counted as last dose.
- **Adverse events of special interest (AESIs)** for ramucirumab include arterial thromboembolic events (ATEs)*, congestive heart failure (CHF)*, fistula (gastrointestinal [GI]* and non-GI), gastrointestinal perforation (non-fistula)*, hemorrhage (also GI hemorrhage as a subcategory and pulmonary hemorrhage [composite term])*, healing complication, hypertension*, infusion-related reaction (IRR) including anaphylactic reaction, liver injury/failure*, proteinuria*, reversible posterior leukoencephalopathy syndrome (RPLS), and venous thromboembolic events*.

Notes:

1. All AESIs are compound level.
2. Each AESI is defined by a set of MedDRA preferred terms (PTs).
 - 2.1. For RPLS, the PTs were directly selected from MedDRA.
 - 2.2. For AESIs marked with *, the PTs were selected from the applicable standardized MedDRA queries (SMQs) v.15.0 or higher.
 - 2.3. For non-GI fistula, all PTs containing the text string “fistula” need be used for analysis.
 - 2.4. For the rest of the AESIs, the PTs were identified through medical review of all unique PTs collected in all ramucirumab studies for compound-level AESIs.
3. Categories of AESIs may be modified as the understanding of the safety of the investigational drug increases. The final list of categories will be reported in the clinical study report (CSR).

- **Consolidated AEs** include abdominal pain, anemia, fatigue, hyperbilirubinaemia, hypercalcaemia, hyperkalaemia, hypermagnesaemia, hypernatraemia, hyperphosphataemia, hypoalbuminaemia, hypocalcaemia, hypokalaemia, hypomagnesaemia, hyponatraemia, hypophosphataemia, intestinal obstruction, leukopenia, myocardial infarction, neuropathy, neutropenia, rash, renal failure, thrombocytopenia, and urticarial.
Note. Consolidated AEs are composite AE terms consisting of synonymous PTs to allow meaningful interpretation of the AE data. Additional consolidated AE categories may be added as needed. The final list of consolidated AE categories will be reported in the CSR.
- **Events of clinical interest (ECIs)** for pembrolizumab include 2 categories:
 1. An overdose of pembrolizumab (≥ 1000 mg [5 times the dose]) not associated with clinical symptoms or abnormal laboratory results
 2. An elevated AST or ALT lab value that is greater than or equal to 3X the upper limit of normal (ULN) and an elevated total bilirubin lab value that is greater than or equal to 2X ULN and, at the same time, an alkaline phosphatase lab value that is less than 2X ULN, as determined by way of protocol-specified laboratory testing or unscheduled laboratory testing.
- **Serious adverse event (SAE)** is defined as any AE that results in one of the following outcomes:
 - death
 - initial or prolonged inpatient hospitalization
 - a life-threatening experience (that is, immediate risk of dying)
 - persistent or significant disability/incapacity
 - congenital anomaly/birth defect

- considered significant by the investigator for any other reason

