5.3.8. Deaths, Serious Adverse Events, and Other Significant Adverse Events

Reasons for deaths will be summarized separately for 1) all deaths, 2) deaths up to 30 days after the last infusion of study treatment, and 3) deaths after 30 days of last infusion of study drug. Reasons of deaths will also be listed.

Serious adverse events (SAEs) will be summarized by PT and repeated for events deemed by the investigator to be possibly related to study medication, with consolidated summary performed if needed. SAEs will be summarized both up to 30 and 90 days after end of therapy. A listing of SAEs will be produced.

In addition, the following analyses will be performed:

- AESIs for ramucirumab by PT
- AESIs for ramucirumab by PT related to study drug
- ECIs for pembrolizumab by PT
- ECIs for pembrolizumab by PT related to study drug
- Listing of AESIs, sorted in the order of phase, cohort, AESI category, PT, and patient identification
- Listing of AEs with outcome of death or discontinuation

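### The term rule for non-GI fistula in SAP 5.2.1.3 does not exclude the GI fistula terms, so the two AESI categories can overlap (minor)

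*SAP*

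**What the plan says.** In SAP 5.2.1.3 (Adverse Event-Related Variables) fistula is one entry in the ramucirumab AESI list, in two parts: "fistula (gastrointestinal [GI]* and non-GI". Only the GI part carries an asterisk. The notes under the list then say how terms are assigned:

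- The general rule: "Each AESI is defined by a set of MedDRA preferred terms (PTs".
- Note 2.2, for the asterisked items: "For AESIs marked with *, the PTs were selected from the applicable standardized MedDRA queries (SMQs) v.15.0 or higher". This covers GI fistula.
- Note 2.3, for the other part: "For non-GI fistula, all PTs containing the text string" 'fistula' are to be used.
- Note 3: "Categories of AESIs may be modified as the understanding of the safety of the investigational drug increases", with the final list of categories given in the study report.

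SAP 5.3.8 plans summaries described as "AESIs for ramucirumab by PT", the same for events related to study drug, and a patient listing sorted by phase, cohort, AESI category, preferred term and patient. The SMQ term list itself is not in either document.

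**The concern.** The list presents GI and non-GI fistula as a split by site. A split works only if each term belongs to one side. Note 2.3 assigns to the non-GI side every preferred term containing the word, and the name of a GI fistula can contain that word as readily as any other. A programmer who follows the note literally would place such a term under non-GI while the SMQ rule also places it under GI.

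What is at stake is the accuracy of one descriptive safety category. Safety and tolerability are the primary objective (SAP 4.1), and the protocol's text on fistula formation (6.9.1.2.1.8) says that a fistula's effect on quality of life depends on its location and extent. Location is what this split is meant to show, so the non-GI label should be true of what sits under it.

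**Working it through.** The documents give no fistula rate and no planned figure for this category, so there is nothing to reproduce. The check is a comparison of the two term sets, followed by a simple illustration of size.

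**Step 1: the sets as written.** Let G be the GI fistula terms from the SMQs (Note 2.2) and S be all preferred terms containing 'fistula' (Note 2.3).

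- GI fistula = G.
- Non-GI fistula as written = S.
- Overlap = G ∩ S, meaning every GI fistula term that contains the string.
- A disjoint split would need non-GI = S minus G.

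**Step 2: whether anything else removes the overlap.**

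- Elsewhere in the same list the SAP writes an exclusion where it wants one: "gastrointestinal perforation (non-fistula". It also states nesting where it wants that, with GI hemorrhage named as a subcategory of hemorrhage. Note 2.3 does neither.
- The count-once rule in SAP 5.3.7 works within a system organ class or preferred term. It does not cover AESI categories.
- Note 3 allows categories to change but does not alter the rule in Note 2.3.
- No order of assignment between the two fistula categories is given in either document.

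**Step 3: which outputs depend on it.**

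- Rows by preferred term: unaffected, because each event is shown under its own term.
- Combined fistula total: unaffected, because G ∪ S and G ∪ (S minus G) are the same set.
- The listing sorted by AESI category, and any non-GI count drawn from it: affected.

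**Step 4: size, for illustration.** Let a be the number of patients whose only fistula is a GI one with a term in G ∩ S. The excess in a non-GI percentage is 100 × a / N. With a = 1 and the planned expansion sizes in SAP 5.1.2:

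| Group | N | Excess per such patient |
|---|---|---|
| Cohort A or B | 15 | 1/15 = 6.67 points |
| Cohort A1, A2, C, D or E | 25 | 1/25 = 4.00 points |
| Cohorts A and B combined | 30 | 1/30 = 3.33 points |
| All expansion cohorts | 155 | 1/155 = 0.65 points |

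With a = 0 the excess is 0.

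**Step 5: how likely the condition is, under an assumption.** The documents give no GI fistula rate. If the rate per patient, p, lay between 0.5% and 3% (an assumption), the chance of at least one GI fistula is 1 − (1 − p)^N:

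- N = 25: 1 − 0.995^25 = 12% up to 1 − 0.97^25 = 53%.
- N = 155: 1 − 0.995^155 = 54% up to 1 − 0.97^155 = 99%.

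These are chances of any GI fistula. The chance of a misclassified one is the same or lower, since the term must also contain the string.

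**The case against.** The best defence is that Note 2.3 is headed by the words non-GI fistula. Notes 2.1 to 2.4 describe where the terms for each AESI come from, so the note can be read as a string search that supplies the remainder once the SMQ has supplied the GI terms. Note 1 says the AESIs are defined at compound level, and Note 2.2 speaks of the SMQ terms as already selected. A term list that separates the two may therefore exist outside the SAP. That is possible and cannot be checked here. It does not settle the matter, because the note says all terms and not the remaining ones, and there is no independent list of non-GI terms for the search to run within: Note 2.3 is the rule that creates it.

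Other parts of the defence stand in full. No stand-alone non-GI fistula rate is named among the planned AESI analyses. The summaries are by preferred term, so a reader of the tables or the listing could see the actual term.

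A reader might infer more than the documents support:

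- **That every GI fistula is double-counted.** This is not shown. Only terms containing the string are caught, and the SMQ list is not available.
- **That the trial's non-GI fistula rate is wrong.** This needs at least one such GI event, the literal reading, and a category-level count that the SAP does not explicitly plan.
- **That the non-GI figures would mostly repeat the GI figures because Schedule 1 enrols gastric-GEJ and biliary cancers.** Neither document gives fistula rates by site.
- **That treatment decisions are touched.** The fistula row of protocol Table JVDF.4 makes no distinction by site.

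**Conclusion.** The point holds as a small fault in a stated rule. Note 2.3, followed literally, makes the GI and non-GI fistula categories overlap, and nothing else in the protocol or SAP separates them. The consequence is possible misclassification in one descriptive safety category, of 4.0 points per affected patient at N = 25 and 6.7 points at N = 15, and nothing if no such event occurs.

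This rests on two assumptions: that the note is programmed as written, and that at least one term in the GI fistula SMQ list contains the string. DLT decisions, discontinuation rules, sample size, power and efficacy are not involved. It is a minor correction.

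**What to change.** Reword Note 2.3 so that non-GI fistula consists of all preferred terms containing the string 'fistula' that are not in the GI fistula SMQ term list. Apply the same exclusion in the AESI term list used for programming, and settle that list and its MedDRA version before database lock. If the compound-level list already separates the two groups, a sentence in the SAP saying so would be enough.

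The cost is one clause in the SAP and one exclusion in the term list. No data collection or clinical procedure changes.
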